The number and percentage of patients who did not complete the treatment due to lack of efficacy or adverse event will be summarized using descriptive statistics, and the time to treatment discontinuation due to lack of efficacy or adverse event will be analyzed using the Kaplan-Meier Survival Analysis method.

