1. STUDY OBJECTIVES AND ENDPOINTS

1.1. Primary and Secondary Study Objectives and Endpoints

The primary and secondary study objectives and endpoints are as follows:

Objectives	Endpoints

The primary objective of the study is to estimate the treatment effect of fremanezumab administered subcutaneously in reducing pain in adult patients with Fibromyalgia (FM).
	
The primary efficacy endpoint is the change from baseline to week 12 in the weekly average of the daily average PI-NRS score over the past 24 hours.

A secondary objective is to evaluate the effect of fremanezumab on other efficacy measures, including pain, quality of life, sleep, fatigue, improvement in health, physical functioning, and mood.
	
The secondary efficacy endpoints are as follows:
 
 • change from baseline to week 12 in the individual components of the Fibromyalgia Impact Questionnaire Revised (FIQR): symptom subscore, impact subscore, and functional subscore score • responder rate of the Patient Global Impression of Change (PGIC) rating (percentage of patients much improved or very much improved) at week 12 • the percentage of patients who experience a $\geq 30\%$ reduction in the weekly average of the daily average PI-NRS score at week 12 • the percentage of patients who experience a $\geq 50\%$ reduction in the weekly average of the daily average PI-NRS score at week 12 • change from baseline to week 12 in the weekly average of the daily worst PI-NRS score over the past 24 hours • change from baseline to week 12 in the Patient-Reported Outcomes Measurement Information System (PROMIS) Sleep Disturbance Short Form (SF) 8a score • change from baseline to week 12 in the PROMIS Physical Function SF12a score • change from baseline to week 12 in the PROMIS Fatigue SF8a score

Objectives	Endpoints
	
 • number (%) of patients who did not complete the treatment (Kaplan-Meier Survival Analysis) due to lack of efficacy

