The total raw score will be calculated as the summation of 8 non-missing scores. The calculated total raw score will be converted into t-score using the scoring table ([PROMIS-Fatigue Scoring Manual](#)). All questions must be answered in order to produce a valid t-score using the scoring table. The analysis will be based on t-score.

The change from baseline to week 12 in the t-score of the PROMIS Fatigue SF8a will be analyzed using MMRM method in manner analogous to the analysis as described in Section 6.3.1. The dependent variable is the change from baseline in the t-score of the PROMIS Fatigue SF8a at weeks 4, 8, and 12 (3 levels). BASE will be the t-score of PROMIS fatigue SF8a from the baseline. Missing will be considered as missing at random. The results from all visits will be presented using descriptive statistics.

Summary statistics will include data from all visits.

6.3.8. Number (%) of Patients Who Did Not Complete the Treatment Due to Lack of Efficacy

Time to treatment discontinuation will be assessed for all patients and will be measured from the date of the first dose of study medication to the date of treatment completion or treatment discontinuation before visit 7. Time to treatment discontinuation is defined as the date of EOT - the date of 1st dosing of IMP + 1. Patients who completed the treatment will be censored at the date of EOT. Patients who did not complete the treatment due to reasons other than lack of efficacy will be censored at the date of ET. Patients who are lost to follow-up will be censored at the date of their last visit.

Time to treatment discontinuation will be analyzed using Kaplan-Meier survival analysis method. Number (%) of patients who do not complete the treatment due to lack of efficacy (the event) and patients censored will be presented. Kaplan-Meier estimates (median time to treatment discontinuation due to lack of efficacy, survival probability at weeks 4, 8, 12 and 16) and survival plot will also be presented.

6.4. [Redacted]

[Redacted]

6.4.1. [Redacted]

[Redacted]

[Redacted]

[Redacted]

• [REDACTED]

[REDACTED]

[REDACTED]

[REDACTED]

[REDACTED]

6.4.2. [REDACTED]

[REDACTED]

[REDACTED]

[REDACTED]

[REDACTED]

6.4.3. [REDACTED]

[REDACTED]

[REDACTED]

[REDACTED]

[Redacted text block]

6.4.4. [Redacted text block]

6.4.5. [Redacted text block]

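### Kaplan-Meier probabilities for lack-of-efficacy discontinuation censor all other stops and so overstate the actual probability; the crude number (%) beside them is not affected

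*SAP*

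**What the plan says.** SAP 1.1 lists as a secondary efficacy endpoint the "number (%) of patients who did not complete the treatment (Kaplan-Meier Survival Analysis) due to lack of efficacy". SAP 6.3.8 makes lack-of-efficacy discontinuation the event and sets three censoring rules:

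- Completers are censored at end of treatment.
- For other stops, "Patients who did not complete the treatment due to reasons other than lack of efficacy will be censored at the date of ET".
- For those lost to follow-up, the last visit is the censoring date.

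On the method, "Time to treatment discontinuation will be analyzed using Kaplan-Meier survival analysis method". The Kaplan-Meier outputs are the "median time to treatment discontinuation due to lack of efficacy, survival probability at weeks 4, 8, 12 and 16", together with a survival plot. The same section also plans a crude summary: "Number (%) of patients who do not complete the treatment due to lack of efficacy (the event) and patients censored will be presented".

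Protocol 9.6.4.3 has the same pairing: "number and percentage of patients who did not complete the treatment due to lack of efficacy or adverse event will be summarized using descriptive statistics". Time to discontinuation is there analysed by Kaplan-Meier. SAP 5.2 tabulates discontinuations by reason.

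Neither document mentions a cumulative incidence or competing-risk estimate. For this endpoint neither names a log-rank test, a hazard ratio, a confidence interval for a difference or a p-value. SAP 2.5.1 and 2.5.2 record that the study was ended early for futility.

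**The concern.** Stopping treatment for an adverse event or another reason rules out stopping later for lack of efficacy. Censoring such a patient removes them from the risk set and in effect shares their remaining probability among those still on treatment. The curve then describes a hypothetical setting in which nobody stops for any other reason. A reader who takes one minus the curve at week 16 as the share of patients who stopped for lack of efficacy will read too high a figure.

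Even the hypothetical reading needs other stops to be unrelated to the later risk of stopping for lack of efficacy. Protocol 4.3 makes that doubtful: where several reasons apply and one is an adverse event, the termination is generally recorded as adverse-event related. Some patients who were also failing on efficacy would then be censored.

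At stake are the reported probabilities and plot of one secondary efficacy endpoint, and what a reader infers by comparing the arms' curves.

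**Working it through.** **Plan's own figures.** The documents give no rate of lack-of-efficacy, adverse-event or other discontinuation, so there is no planned figure to reproduce for this endpoint. The only planning figure is the precision statement in SAP 2.4 (SD 2.2, 80 per arm, 95% CI half-length below 0.74 with probability at least 90%). It reproduces: expected half-length = 1.975 × 2.2 × √(2/80) = 0.687, and P(half-length < 0.74) = 0.918. It does not enter the analysis below, except that 80 per arm sets the scale of sampling error.

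**Formula.** Assume constant cause-specific hazards over 16 weeks. Let a be the true cumulative incidence of stopping for lack of efficacy and b that of stopping for other reasons.

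- Total cumulative hazard: H = −ln(1 − a − b)
- Lack-of-efficacy share: h = H × a/(a + b)
- Planned estimate: 1 − KM = 1 − exp(−h)
- A cumulative incidence estimate returns a itself.

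**One arm.** All rates are assumed.

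| a | b | H | h | 1 − KM | Relative excess | Excess patients per 80 |
|---|---|---|---|---|---|---|
| 10% | 10% | 0.2231 | 0.1116 | 10.56% | 5.6% | 0.45 |
| 10% | 20% | 0.3567 | 0.1189 | 11.21% | 12.1% | 0.97 |
| 10% | 30% | 0.5108 | 0.1277 | 11.99% | 19.9% | 1.59 |
| 15% | 10% | 0.2877 | 0.1726 | 15.85% | 5.7% | 0.68 |
| 15% | 20% | 0.4308 | 0.1846 | 16.86% | 12.4% | 1.49 |
| 15% | 30% | 0.5978 | 0.1993 | 18.07% | 20.5% | 2.45 |

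The relative excess depends mainly on b. With 5% other stops it is about 3%. A simulation of 200,000 patients at a = 10%, b = 20% gave a crude proportion of 10.1% against 1 − KM of 11.3%, which confirms that the crude figure is not inflated.

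**Two arms.** Differences are placebo minus active, with 15% against 10% truly stopping for lack of efficacy (true difference 5.0 points).

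- Equal other stops, 20% in each arm: 16.86 − 11.21 = 5.65 points, slightly stretched.
- More other stops on active (placebo 10%, active 30%): 15.85 − 11.99 = 3.86 points, shrunk.
- More other stops on placebo (placebo 30%, active 10%): 18.07 − 10.56 = 7.51 points, enlarged.

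With 10% truly stopping for lack of efficacy in both arms, other stops of 10% and 30% produce a spurious difference of 11.99 − 10.56 = 1.43 points. Equal other stops leave a zero difference at zero.

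**Scale of noise.** At 80 per arm the standard error of a difference between two proportions near 10% is √(2 × 0.10 × 0.90/80) = 4.7 points. For 15% against 10% it is √(0.15 × 0.85/80 + 0.10 × 0.90/80) = 5.2 points.

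**Sponsor termination.** In the same simulation setting, with an assumed 25% of patients given a sponsor stop at a random time in follow-up, the crude proportion was 8.9%, the Aalen-Johansen estimate 10.1% and 1 − KM 11.3%, against a true 10%. Sponsor stops were treated as censoring for the last two.

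**The case against.** The strongest defence is that the endpoint is worded as a number (%). SAP 6.3.8 reports that count together with the number censored, and censoring cannot inflate a count. This stands. A reader might infer that the plan overstates how many patients stop for lack of efficacy, but the documents support that only for the Kaplan-Meier probabilities and plot.

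Second, no formal comparison of arms is planned, so no test can be biased. This also stands. A reader might infer that a true advantage of fremanezumab would be shrunk. That needs more other-reason stops on active treatment, and the documents report no rates by arm. The opposite imbalance enlarges the difference, and balance stretches it slightly.

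Third, Kaplan-Meier with this censoring is a legitimate description of the cause-specific hazard, and SAP 5.2 shows other-reason stops by arm. Both are true, but nothing in SAP 6.3.8 tells the reader to interpret the curve in that way.

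Fourth, disagreement between the curve and the crude percentage does not by itself show an error. With true administrative censoring, a correct estimator also differs from the crude percentage. This stands, and it cuts the other way too: because the study was ended early, the crude percentage may be too low for any patients the sponsor stopped, so it is not a full substitute.

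**Conclusion.** The point holds in a limited form. The planned probabilities at weeks 4, 8, 12 and 16 and the plot overstate the actual probability of stopping for lack of efficacy whenever some patients stop earlier for other reasons. With about 10% truly stopping for lack of efficacy, the relative overstatement at week 16 is about 6%, 12% or 20% for 10%, 20% or 30% other stops. At 20% that is about one patient in 80. These sizes rest on assumed rates and constant hazards, whereas the direction does not depend on the rates chosen.

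Effects on the descriptive contrast between arms can go either way. In the cases worked they lie between 0.65 and 2.51 points (5.65 and 7.51 against a true 5.0), which is below the standard error of about 5 points. This is a minor issue of estimation and labelling on a descriptive secondary endpoint. It has no bearing on the primary analysis or the sample size.

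**What to change.** - Report the Aalen-Johansen cumulative incidence of lack-of-efficacy discontinuation by arm at weeks 4, 8, 12 and 16. Adverse-event and other patient-level discontinuations are competing events. Completion of treatment and sponsor termination of the study are censoring.
- Do not code every stop other than lack of efficacy as competing. Counting sponsor stops as competing would roughly return the crude percentage, with the same understatement.
- State explicitly how patients lost to follow-up are classified.
- Keep the crude number (%). If the Kaplan-Meier curve is kept, label it as cause-specific and add a footnote that one minus the curve is not the proportion who stopped.
- List the change in SAP Section 18, which now shows none. SAP 2.5.2 allows for SAP amendments approved before database lock.

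The programming is small: an event code that separates the reasons (EVENTCODE= in PROC LIFETEST) and a check that sponsor termination can be identified among the recorded reasons. The downside is a departure from the Kaplan-Meier method named in the endpoint wording of both documents. The change does not repair how reasons are recorded when several apply.

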7. MULTIPLE COMPARISONS AND MULTIPLICITY

No multiplicity adjustment is planned for this study.

8. SAFETY ANALYSIS

8.1. General

The safety analysis set will be used for all safety analyses. Summaries will be presented by treatment group as actually received unless otherwise stated.

In the Study TV48125-PN-20028 protocol amendment 04, the data collections had been changed:

- Some data are not collected as they were prior to protocol amendment 04 at some visits; for example, clinical laboratory data are no longer collected at visits 4 and 5.
- Follow-up visit was removed

This section reflects data collections in the study including data collected prior to Study TV48125-PN-20028 protocol amendment 04. For by-visit summaries, all data collected in the study will be summarized.

8.2. Duration of Exposure to Study Drug

Duration of exposure to study drug (days) for the individual patient is the number of days patient received drug (last day of study drug – first day of study drug + 28).

Number (%) of patients receiving 1 dose, 2 doses, 3 doses, and 4 doses and duration of treatment (days) will be summarized by treatment group using descriptive statistics.

8.3. Adverse Events

An adverse event (AE) is any untoward medical occurrence in a patient administered a pharmaceutical product which does not necessarily have to have a causal relationship with this treatment.

For recording of AE, the study period is defined for each patient as the time period from signature of the informed consent form (ICF) to the end of the follow-up period or the early termination visit for patients who discontinued from the study for any reason. Any AE occurring on or after the first dose of study drug is considered a treatment-emergent AE (TEAE). All AE summaries will be conducted for TEAEs.

The following are considered protocol-defined adverse events of special interest (AESI) to be sent to the sponsor's Global Patient Safety and Pharmacovigilance (GPSP) Department for evaluation:

- ophthalmic-related adverse events of at least moderate severity, as determined by the investigator
- severe hypersensitivity reactions

All AEs will be coded using MedDRA. The incidence of AEs will be summarized using descriptive statistics by SOC and preferred term (PT). Each patient will be counted only once in each PT or SOC category for the analyses of safety.

Statistical Analysis Plan

Summaries will be presented for all AEs (overall and by severity), AEs determined by the investigator to be related to test IMP (ie, reasonable possibility) (defined as related or with missing relationship) (overall, overall by severity, serious AEs, and AESI), serious AEs, AESI, AEs causing discontinuation from treatment, AEs causing early termination from the study, injection site AEs, and AEs leading to death.

Listings of AEs, AESI, serious AEs, injection site AEs, and AEs leading to early termination will be presented separately.

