7.1.2. Recording and Reporting of Adverse Events

For recording of adverse events, the study period is defined for each patient as the time period from signature of the ICF to the end of the study or the ET visit for patients who discontinue from the study for any reason. Symptoms or signs of medication withdrawal during the weaning period should be recorded as a medication withdrawal adverse event. The period for reporting treatment-emergent adverse events is defined as the period after the first dose of IMP is administered.

All adverse events that occur during the defined study period must be recorded both on the source documentation and the eCRF, regardless of the severity of the event or judged relationship to the IMP. For serious adverse events, the serious adverse event form must be completed, and the serious adverse event must be reported immediately (Section 7.1.5.3.1). The investigator does not need to actively monitor patients for adverse events after the defined period.

At each contact with the patient, the investigator or designee must question the patient about adverse events by asking an open-ended question such as “Have you had any unusual symptoms or medical problems since the last visit? If yes, please describe.” All reported or observed signs and symptoms will be recorded individually, except when considered manifestations of a medical condition or disease state. A precise diagnosis will be recorded whenever possible. When such a diagnosis is made, all related signs, symptoms, and any test findings will be recorded collectively as a single diagnosis on the eCRF and, if it is a serious adverse event, on the serious adverse event form.

The clinical course of each adverse event will be monitored at suitable intervals until resolved, stabilized, or returned to baseline; or until the patient is referred for continued care to a health care professional; or until a determination of a cause unrelated to the IMP or study procedure is made.

The onset and end dates, duration (in case of adverse event duration of less than 24 hours), action taken regarding IMP, treatment administered, and outcome for each adverse event must be recorded both on the source documentation and the eCRF.

The relationship of each adverse event to IMP and study procedures, and the severity and seriousness of each adverse event, as judged by the investigator, must be recorded as described below.

Further details are given in the Safety Monitoring Plan.

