4.4. Study Days and Visits

Study visits are detailed in Table 1.

Table 1: Study Visits

Study period	Screening Period (Up to 5 weeks [17 to 35 days])			Double-Blind Treatment Period (16 weeks)				
	Screening Visit	Phone Contact (Washout)	Baseline Assessment Period	Randomization (Dose 1)	Dose 2	Dose 3	Dose 4	
Visit	V1	Phone Contact	V2 (BAPS Visit)	V3	V4	V5	V6	V7 (EOT/ EOS or ET)
Day and allowed time windows	Week-5 Day -35	Day -33 through Day -15	Day -14 (±2 days)	Day 1	Day 29 ±7 days	Day 57 ±7 days	Day 85 ±7 days	Day 113 ±7 days

BAPS=Baseline Assessment Period Start; EOT=End of treatment; ET=Early termination; EOS=End of Study.

There was a follow-up period (14 weeks) in the Study TV48125-PN-20028 protocol prior to amendment 04. The data collected in the follow-up period will be listed.

Study days will be numbered relative to the first day of IMP administration. The start of treatment (Day 1 at Visit 3) is defined as the date on which a patient takes the first dose of IMP, as recorded on the study drug administration CRF. Days will be numbered relative to treatment start (ie, ..., -2, -1, 1, 2, ...; with day 1 being the first day of IMP administration and day -1 being the day before the first day of IMP administration).

‘Last Assessment’ will be derived for analysis purposes and is defined as the last observed postbaseline data, excluding the follow-up visit. For by-visit summaries, data from the ET visit will be included as one of the visits indicated in the database.

For data collected daily on e-diary, analysis weeks (week 1, week 2, ..., etc.) will be derived for the purpose of efficacy endpoint analyses. Details are provided in Section 6.1.2.

Statistical Analysis Plan

Data collected after week 12 will be included in descriptive summaries but will not be included in any inferential analyses.

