8.7. Vital Signs

Vital signs (blood pressure [systolic/diastolic], respiratory rate, oral body temperature, and pulse) will be measured at the time points detailed in Table 1 in the study protocol.

Summary statistics for vital signs (blood pressure [systolic/diastolic], respiratory rate, oral body temperature, and pulse) will be presented at baseline, week 4, week 8, week 12, week 16 (end of treatment), week 30 (end of study), and last assessment. Vital signs values and changes from baseline to each visit will be summarized using descriptive statistics.

Summaries of potentially clinically significant abnormal values will include all postbaseline values (including scheduled, unscheduled, and withdrawal visits). The incidence of potentially clinically significant abnormal values will be summarized using descriptive statistics with the criteria specified in Table 5. Systolic and diastolic blood pressure will be included in all summaries.

Table 5 specifies the criteria for identifying vital signs as potentially clinically significant abnormal values. Note that in order to qualify as potentially clinically significant abnormal, a value needs to meet both criteria below: ie, have a value beyond the criterion value and a change of at least the magnitude specified in the change relative to baseline column.

Table 5: Criteria for Potentially Clinically Significant Vital Signs

Vital Sign	Criterion value	Change relative to baseline
Pulse	≥120 bpm	Increase of ≥15
	≤50 bpm	Decrease of ≥15
Systolic blood pressure	≥180 mm Hg	Increase of ≥20
	≤90 mm Hg	Decrease of ≥20
Diastolic blood pressure	≥105 mm Hg	Increase of ≥15
	≤50 mm Hg	Decrease of ≥15
Respiratory rate	<10 breaths/min	
Body temperature	≥38.3°C	Change of ≥1.1°C

bpm=beats per minute

Listings for potentially clinically significant abnormal laboratory data will be presented.

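### SAP 8.3 pools adverse events over two observation windows: up to 30 weeks for some early patients, 16 weeks for the rest

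*SAP*

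**What the plan says.** SAP 8.3 defines a treatment-emergent event by its start, "Any AE occurring on or after the first dose of study drug is considered a treatment-emergent AE (TEAE", and makes that the basis of every table: "All AE summaries will be conducted for TEAEs". The sentence before it gives the recording period, which runs from "signature of the informed consent form (ICF) to the end of the follow-up period or the early termination visit". Protocol 7.1.2, revised by Amendment 04, ends recording differently: "the time period from signature of the ICF to the end of the study or the ET visit". The protocol's own treatment-emergent definition also has a start and no end. The SAP's introduction says the SAP prevails where the two differ.

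On follow-up data, SAP 2.1 notes that a 14-week follow-up existed before Amendment 04. Sections 2.1 and 4.4 both state: "The data collected in the follow-up period will be listed". SAP 8.1 says of the safety section: "This section reflects data collections in the study including data collected prior to Study TV48125-PN-20028 protocol amendment 04", and adds that by-visit summaries use everything collected. SAP 8.7 summarises vital signs at "week 16 (end of treatment), week 30 (end of study), and last assessment", among other visits, and counts potentially clinically significant values over all postbaseline values. Follow-up is excluded in two places only: the derived last assessment (4.4) and efficacy summaries that use the last visit (6.1). No section gives a treatment-emergent cut-off, an exposure-adjusted AE rate, or an AE summary split by amendment.

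The protocol's amendment history gives 68 patients randomised at Amendment 04 (16 June 2020) and at its Revision 01 (25 June 2020), and 153 at Amendment 05 (10 August 2021). The planned total was 240.

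**The concern.** The percentage of patients with at least one event rises with the time they are watched. Under SAP 8.3 as written, an early patient who went through follow-up can be counted for an event at week 28. A later patient cannot, because nobody was asking by then. Both sit in the same denominator.

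Safety and tolerability is a stated secondary objective, and a reader will naturally take the AE tables of a study with a 16-week treatment period as 16-week results. If the windows are mixed, the percentages describe no defined period. They also depend on how many patients happened to enrol before a protocol change, and they cannot be set cleanly beside other studies. The same applies to the incidence of potentially clinically significant vital signs, since the former follow-up visit supplies extra postbaseline values for early patients only.

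**Working it through.** **1. The two windows.** Treatment is 16 weeks (SAP 2.1) and the former follow-up 14 weeks (SAP 2.1): 16 + 14 = 30, which reproduces the week 30 in SAP 8.7. By study day, the former last visit was day 211 (protocol change log, Amendment 03) and Visit 7 is day 113: (211 − 1)/7 = 30.0 and (113 − 1)/7 = 16.0.

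**2. How many patients could have the long window.** The ceiling is 68, the number randomised when Amendment 04 was issued. The dates suggest fewer completed follow-up:

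- Day 211 falls 210 days after first dose. To reach it by 25 June 2020 a patient needed a first dose by 28 November 2019 (by 19 November for 16 June).
- Day 113 falls 112 days after first dose. To finish treatment and enter follow-up by 25 June 2020 a patient needed a first dose by 5 March 2020.
- Nobody had been randomised at Amendment 03 (22 July 2019). Protocol 1.2.2 estimates 4 fibromyalgia patients exposed by 30 August 2019. Protocol Appendix O refers to patients still in screening or baseline on 26 March 2020.

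The documents give neither the number followed nor the dates on which sites implemented the amendment. I take half of the 68 (34) as a working assumption and show the ceiling beside it.

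**3. Size of the distortion.** The documents give no AE rates, so the 16-week risk p16 is assumed over 5% to 50% with a constant hazard. With f the share of patients who have the full 30 weeks:

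- p30 = 1 − (1 − p16)^(30/16)
- pooled risk = (1 − f) × p16 + f × p30
- excess over a common 16-week window = f × (p30 − p16)

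Example with f = 34/153 = 0.222 and p16 = 0.50: p30 = 1 − 0.5^1.875 = 0.727, and the excess is 0.222 × 0.227 = 0.051, so the table shows 55.1% instead of 50%.

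| p16 | p30 | Excess, f = 34/153 | Excess, f = 68/240 | Excess, f = 68/153 |
|---|---|---|---|---|
| 5% | 9.2% | 0.9 points | 1.2 | 1.9 |
| 10% | 17.9% | 1.8 | 2.2 | 3.5 |
| 20% | 34.2% | 3.2 | 4.0 | 6.3 |
| 30% | 48.8% | 4.2 | 5.3 | 8.3 |
| 50% | 72.7% | 5.1 | 6.4 | 10.1 |

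The mean window with f = 34/153 is 16 + 14 × 0.222 = 19.1 weeks.

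**4. Effect between arms.** If f differed by 10 percentage points between two arms by chance, the spurious difference would be 0.10 × (p30 − p16): 0.8 points at p16 = 10%, 1.9 at 30% and 2.3 at 50%.

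**The case against.** The strongest reply is that counting every recorded post-dose event is a conservative safety choice, and that a cut at Visit 7, about 4 weeks after the last dose, could hide drug effects. The protocol supports this: it cites a long half-life (3.3) and runs contraception and blood-donation limits for 6 months after dosing. This stands as a reason not to drop follow-up events or call them off-drug noise. It does not justify pooling them with patients who had no follow-up.

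Several stronger readings are tempting, and the documents do not support them:

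- *The window is unlimited.* The treatment-emergent sentence has no end, but the recording period before it does. The window is bounded; the bound differs by amendment.
- *All 68 early patients had 30 weeks.* That requires first doses by late November 2019 or a long delay in implementing the amendment, and the documents show neither. The right-hand columns of the table are ceilings.
- *The excess is as large as a constant hazard implies.* Protocol 1.3.1 names administration-site reactions as the most common events in migraine patients. Follow-up had no injections and one visit in 14 weeks, so the true excess is probably smaller.
- *The arms are biased.* Randomisation is concurrent and 1:1:1, so the mix is balanced in expectation. Only chance imbalance remains, and it is small (step 4).
- *The week-30 vital-sign row mixes windows.* A by-visit row holds only patients seen at that visit, so it does not.
- *The SAP flatly contradicts itself.* Sections 2.1 and 4.4 promise a listing without saying it is the only output. The texts pull in different directions and need reconciling, which is less than a contradiction.

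It is also fair that this is a proof-of-concept study stopped for futility, with descriptive safety tables and separate AE listings. That limits the stakes.

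**Conclusion.** The point holds. Following SAP 8.3 as written, the pooled AE percentages combine up to 30 weeks of observation in some early patients with 16 weeks in the others. Protocol 7.1.2 does not cure this, because the SAP prevails and also takes in pre-Amendment-04 data. The potentially clinically significant vital-sign incidence shares the fault.

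The damage is to the meaning of the absolute percentages. The excess is about 1 to 5 points if about half of the 68 had full follow-up, on a total of 153, assumed 16-week risks of 5% to 50% and a constant hazard. It would be less for injection-related events, and less with a larger total. The mixing of windows follows from the text. The size rests on those assumptions, because the number of patients actually followed is not in the documents. This is a worthwhile, inexpensive correction, and the safety comparison between arms is not put in doubt.

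**What to change.** Before database lock:

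- In SAP 8.3, state the treatment-emergent window. Base the main pooled AE tables on onset from first dose through Visit 7 or the ET visit.
- Tabulate events with onset in follow-up, including serious events, events of special interest and deaths, in a separate table for pre-Amendment-04 patients with its own denominator, so that none is dropped.
- Apply the same window to the potentially clinically significant vital-sign incidence in SAP 8.7. The week-30 by-visit row may stay if shown with its own n.
- Align the recording period in SAP 8.3 with protocol 7.1.2. Name Visit 7 explicitly, since protocol 3.1 also defines end of study as the last visit of the last patient. Retain a note that pre-Amendment-04 patients could be followed longer.
- Reconcile the listing statements in SAP 2.1 and 4.4 with 8.1 and 8.7.

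The cost is a few sentences, a date filter and one extra table. The headline percentages will be slightly lower than under the present text, and no safety data are lost.
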